6.2 Fidelity

6.2.1 INTERVENTIONIST TRAINING AND TRACKING

To ensure consistent administration of the intervention, fidelity will be monitored through structured observation of the sessions (VR and Zoom) and standardized procedures for survey administration. For VR sessions, we will collect information to confirm adherence to the session protocol, including session duration, participant engagement, and any technological challenges encountered (such as WiFi outages in the community or adult child's home). Resident and adult child surveys will be monitored for completeness, response rates, and all research assistants will be carefully trained in survey administration to ensure accurate data collection.

6.3 Measures to Minimize Bias: Randomization and Blinding

Stratified Block Randomization Schedule (created with R “randomizeR” package):

- Strata = 4 (UCSB/Rendever x MCI/Dementia)
- Groups (VR/Zoom) = 2 | Block size = 4 (resulting in 6 possible combinations to draw from)
- Iterations (sequences) = 12 | 12 sequences of 4 = 48 subjects
- Results = 48 subjects per strata (equal allocation to conditions)
- Total N = 48 subjects x 4 strata = **192 dyads**

“A” = VR “B” = Zoom

UCSB – MCI	UCSB – DEMENTIA
[1] "A" "B" "B" "A"	[1] "B" "A" "B" "A"
[2] "A" "B" "A" "B"	[2] "B" "A" "A" "B"
[3] "B" "A" "A" "B"	[3] "B" "A" "B" "A"
[4] "B" "A" "A" "B"	[4] "B" "A" "B" "A"
[5] "B" "A" "A" "B"	[5] "B" "B" "A" "A"
[6] "B" "A" "B" "A"	[6] "B" "A" "B" "A"
[7] "B" "A" "B" "A"	[7] "B" "A" "A" "B"
[8] "A" "B" "A" "B"	[8] "A" "A" "B" "B"
[9] "B" "B" "A" "A"	[9] "B" "A" "B" "A"
[10] "B" "A" "A" "B"	[10] "B" "A" "B" "A"
[11] "A" "A" "B" "B"	[11] "A" "B" "A" "B"
[12] "B" "B" "A" "A"	[12] "A" "A" "B" "B"

RENDEVER – MCI	RENDEVER – DEMENTIA
[1] "B" "B" "A" "A"	[1] "A" "A" "B" "B"
[2] "B" "A" "B" "A"	[2] "A" "B" "B" "A"
[3] "B" "A" "A" "B"	[3] "A" "B" "B" "A"
[4] "A" "B" "A" "B"	[4] "B" "B" "A" "A"
[5] "B" "A" "A" "B"	[5] "B" "A" "B" "A"
[6] "A" "A" "B" "B"	[6] "A" "A" "B" "B"
[7] "B" "A" "B" "A"	[7] "B" "A" "B" "A"
[8] "A" "B" "A" "B"	[8] "A" "A" "B" "B"
[9] "B" "B" "A" "A"	[9] "B" "A" "A" "B"
[10] "B" "B" "A" "A"	[10] "B" "A" "B" "A"
[11] "B" "A" "A" "B"	[11] "B" "A" "A" "B"
[12] "B" "B" "A" "A"	[12] "A" "A" "B" "B"

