4.1 Overall Design

Purpose of the clinical trial: The virtual reality (VR) program, Rendever, enables older adults in senior living communities to maintain important family relationships, engage fully with life, and reconnect with their past, regardless of physical location, through its advanced networking and live streaming capabilities. This Phase II project will continue to refine the long-distance features of Rendever, while expanding the scientific goals of the project by testing the immediate and longer-term impact of Rendever on the quality of life of residents and their adult children in an experimental design. The study will also continue to investigate whether residents' responses to the VR depend upon their level of cognitive impairment.

Study Design: The design of this study is a 2 (Intervention Group: Virtual Reality vs. Active Control) x 2 (Level of Cognitive Impairment: MCI vs. AD/ADR) x Time (7 time points) design. Participants will be older adults (age 50+) with mild cognitive impairments (MCI) or mild to moderate Alzheimer's Disease or related dementias (AD/ADR) who reside in senior living communities, and an adult child who lives at a distance. Residents will participate from a private room located in their senior living community. Adult children (age 18+) will participate from their own home, at least 45 minutes driving distance away. Resident-adult child dyads will be randomly assigned to an intervention group (Virtual Reality vs. Control) using a random number generator. Dependent variables will include measures of quality of life (quality of life, thriving, depression, mental health, positive and negative affectivity, loneliness, and social connection), family bonding (closeness, satisfaction, communal coping), and caregiver guilt (guilt, stress, and burden) assessed through surveys and interviews over the 4-month study period. Secondary outcome measures will include positive engagement *during the technology sessions* (positive affect, engagement with the technology and with the adult child while using it, emotional closeness) measured through surveys, interviews, and observational methods during the intervention phase of the study.

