5.5 Strategies for Recruitment and Retention

Planned distribution of subjects by sex/gender, race, and ethnicity:

Participants will be 192 resident-adult child dyads recruited from 12 senior living communities (approximately 16 dyads per community). Half of the residents (age 50+) will have mild cognitive impairment (MCI) and half will have mild to moderate Alzheimer's disease and Alzheimer's disease related dementias (AD/ADR). Half of the residents will be recruited in California by the research team at UCSB and half will be recruited in Boston by the Rendever research team. Residents will be recruited from 6 communities in or within 30 minutes of Santa Barbara and 6 communities near Boston.

Recruitment efforts will be extended to additional communities if additional participants are needed, or if doing so would increase sample diversity. Adult children (age 18+) will participate remotely, and may reside anywhere in the world. The average age of residents across the 12 communities is 87. Most communities include independent living, assisted living, and memory care programs. Residents from all three programs will be recruited for the study if they meet eligibility requirements. The communities do not have precise data on residents' levels of cognitive impairment, but it is estimated that 29% of residents have MCI and 40% have AD/ADR.

The demographic makeup of the participating communities is majority female (approximately 70%) and majority white (approximately 85%), with small percentages of Hispanic (5.3%), Black (2.2%), and Non-Hispanic Other (6%) groups. Based on the demographic features of the participating communities, the planned distribution of subjects by sex, race, and ethnicity will be a function of these underlying features and efforts to increase the diversity of our sample by oversampling residents who are male and/or members of under-represented racial and ethnic groups.

With respect to gender, because female residents outnumber male residents by approximately two to one in senior living communities nationally, and in the communities participating in the study, we anticipate that our sample will include more female than male residents. We plan to over-sample male residents, resulting in a planned enrollment of 80 percent female, 20 percent male residents in the sample.

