Rationale for proposed exclusion sex/gender or racial/ethnic groups:

No participants will be excluded based upon sexual identity, sexual orientation, gender, or racial/ethnic identification.

Recruitment Plan: Following successful recruitment procedures developed in the Phase 1 pilot study, the recruitment process will be conducted in several steps.

Step 1: Letters to the families of the residents will be emailed, describing the study and letting them know that, if they qualify, their family might be invited to participate in the study in the near future. The letter will also give them contact information for the researchers so that they can opt out of the study if they prefer not to be contacted.

Step 2: The Director at each community will announce the study to residents via email, flyers, and community newsletters. Directors will also announce the study at large gatherings (e.g., monthly community meetings, movie nights), where researchers will be present to introduce themselves and answer questions. Residents will be invited to contact the researchers (in person, via phone, or email) if they are interested in learning more. The research team will also hold community meet-and-greet events, where they will pass out flyers (in English and Spanish, where relevant) and gather names of interested residents.

Step 3: Directors and key staff of the communities will assist in identifying eligible residents (screening for eligibility).

Step 4: Once identified, potentially eligible residents will be invited to talk with the researchers (in the resident's room or apartment, or in another private space if preferred) to determine if they are interested in participating, and verify that they are eligible to participate. The researchers will explain the purpose and procedures of the study and gather initial verbal consent to participate. At this time, researchers will administer the MMSE to verify eligibility. If a resident's ability to consent is uncertain, the researcher will complete an IRB-approved screener assessing their decision-making capacity to consent, and consent will be obtained from the resident's legal guardian as needed.

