8.2 Safety Assessments

SAFETY PLAN

1. Complete Screening Document (Staff at community)
2. MMSE-2 (UCSB/Rendever senior personnel) & AD8 (adult child completes)
3. All proper levels of consent are gathered—consent is also gathered again every time before VR begins if resident has mild or moderate dementia
4. Ask staff to identify three things that might trigger a resident (if he/she has dementia) and three things that typically calm him/her.
5. Train staff on what the VR is like (try on headsets)
6. Who is the clinician/staff member on location that day in the event that there is an adverse reaction? Gather name and phone number/schedules.
7. Senior personnel (grad student, post doc, faculty) will always be operating the VR with the resident if they have dementia.
8. Training with the adult child on VR and how to communicate with parents ahead of time.
9. Trial run with the VR right before it begins to assess how it feels
10. Check in with the resident and adult child throughout the VR sessions.
11. We will also carefully monitor any hallucinations, seizures, or dizzy spells that residents experience by asking staff members if there are any concerns and on what day. If we believe the VR is connected to any hallucinations or seizures, we can discuss the possibility with the family of removing them from the study.

Safety Plan if there is an adverse reaction:

1. Ask to take off their headset and remove it for them.
2. Turn off the sound on the headset and listen to the resident. Try not to persuade them that their feelings aren't real/or are incorrect.
3. Ask how they are feeling and provide comfort.
4. If they are okay, ask if they would still like to continue by viewing the experience from the tablet with their adult child instead of the VR.
5. If they are feeling dizzy, confused, beginning to feel ill, ask if they would like a drink of water or like to lie down.
6. If they are still agitated, remembering the list of things that tend to calm the resident (e.g., taking a walk, a picture, a specific staff member, a specific area that provides comfort)
7. If the researcher is not able to calm the resident, the researcher will ask the staff member on site that day to come over and help calm them.
8. If the adult child is also distressed, the researcher will ask the dementia expert on the grant ([name]) to follow-up with the adult child (if the adult child would like additional information on coping strategies).

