10.1.1.2 Consent Procedures and Documentation

1: Once identified, potentially eligible residents will be invited to talk with the researchers (in person) to determine if they are interested in participating, and verify that they are eligible to participate. The researchers will explain the purpose and procedures of the study and gather initial verbal consent to participate. At this time, researchers will administer the MMSE-2 to verify eligibility. If a resident's ability to consent is uncertain, the researcher will complete an IRB-approved screener assessing their decision making capacity to consent (see Evaluation of Decision-Making Capacity for Consent to Act as a Research Subject below), and consent will be obtained from the resident's legal guardian as needed. If the resident has dementia, the researcher will collect verbal consent, and consent will also be obtained from the resident's adult child (who would be participating) and legal guardian (if different from the adult child).

2: Contact information for an adult child with whom they would like to participate will be requested from eligible residents. If the resident does not have the contact information, the researchers will attempt to get this information from the Director of the senior living community. If the resident has more than one

eligible adult child, the researcher will randomly select from the list of eligible adult children. Researchers will call the adult child, explain the study, and gather initial verbal consent. The adult child will also complete the 8-item Informant Interview to Differentiate Aging and Dementia measure (AD8) to provide additional verification of the resident's (their parent's) dementia status. This additional information will be valuable because seniors can become accustomed to cognitive tests, making their MMSE-2 scores unreliable indicators of their level of dementia.

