3: Once all initial verbal consents are received, the resident-adult child dyad will be enrolled in the study. Participants will then be scheduled to complete the baseline survey. Prior to the survey, residents and adult children will complete the formal consent process. Residents will be given written consent forms to sign. In addition, a consent script will be read out loud to residents with mild to moderate dementia (and any other residents who request it) to ensure they understand the study procedures and associated risks and safeguards. Adult children will be emailed an online link to a digital consent form and a baseline survey the week before the first VR/Zoom session. If applicable, the resident's legal guardian will be emailed a link to an online, digital consent form.

4: Continuing consent will be obtained from residents with mild to moderate dementia before beginning each of the VR/Zoom sessions using a verbal consent "check-list" (created and approved by the IRB for the Phase 1 pilot study) whereby the researcher states the purpose of the study, what will happen, the risks, and the benefits in very plain language and asks the resident if they understand each question (see Evaluation of Decision-Making Capacity for Consent to Act as a Research Subject below). If the resident is capable and competent at answering the questions, and is alert and oriented to their surroundings and what will happen during the VR/Zoom session, the resident may participate in the session. If the resident is unable to answer the questions and/or is not alert and oriented to their surroundings, or if the resident reports they do not want to participate, then the session will not proceed that day. The researchers will speak with the Director of the senior living community, adult child, and later with the resident to make a determination whether or not the family should continue in the study. If the resident or adult child wants to stop the study, they may do so at any time.

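### Does the allocation list printed in section 6.3, with no stated concealment step or MCI/dementia rule, call for a change to the plan?

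*Combined protocol and SAP*

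**What the plan says.** Section 6.3 of the combined protocol and SAP gives a "Stratified Block Randomization Schedule (created with R" package, four strata (two sites by two impairment levels) and "Block size = 4 (resulting in 6 possible combinations to draw from"). It then prints the arm key and the ordered list for each stratum. Section 4.1 adds that dyads "will be randomly assigned to an intervention group (Virtual Reality vs. Control) using a random number generator". The schedule in section 1.3 marks randomization in the consent column.

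The site teams recruit: in section 5.5, half the residents come from California through the university team and "half will be recruited in Boston by the Rendever research team". On cognitive testing, section 5.5 says "At this time, researchers will administer the MMSE to verify eligibility", and the safety plan in section 8.2 lists "MMSE-2 (UCSB/Rendever senior personnel) & AD8 (adult child completes"). Section 10.1.1.2 explains that the AD8 was added because residents can get used to cognitive tests, "making their MMSE-2 scores unreliable indicators of their level of dementia". The same section then says "Once all initial verbal consents are received, the resident-adult child dyad will be enrolled in the study".

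No section reviewed names a custodian for the list, a release step, or a cut between MCI and dementia. A few sections, among them 10.1.5, were not in the copy reviewed, so the absence is limited to the text that was.

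**The concern.** A complete ordered list with its key, printed in the protocol, is what allocation concealment is meant to keep from the people who enrol. If recruiting staff had it, the order in which residents were approached, the timing of enrolment, or the stratum given to a borderline resident could have depended on the coming arm.

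The two gaps would reinforce each other. With no written rule for combining MMSE-2 and AD8, the stratum label leaves some room for judgement, and the label decides which list is read next. The label is also the moderator in Aim 2.

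At stake would be the primary VR versus Zoom comparison, which is open-label, largely self-reported and planned around a small effect (d = 0.2). Adjusting for baseline would correct only for what baseline measures.

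**Working it through.** **1. The plan's own figure.** From section 6.3: 4 strata × 12 blocks × 4 = 192 dyads. A count of the printed list agrees. All 48 blocks hold two A and two B, each stratum is 24:24, and the total is 96:96, matching section 9.2. The number of block orders is 4!/(2!·2!) = 6, as stated. The list is sound as a randomization schedule.

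**2. Predictability with the list in hand.** 192/192, but only if the person enrolling had access to it.

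**3. Predictability without the list**, knowing the block size and every earlier assignment in the stratum. The last slot of each block is certain. The third slot is also certain when a block opens AA or BB. Counting ties as 0.5, a block that opens AB or BA gives 0.5 + 1 + 0.5 + 1 = 3 correct guesses. One that opens AA or BB gives 0.5 + 0 + 1 + 1 = 2.5.

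| Stratum | Blocks opening AA/BB | Certain | Best guess |
|---|---|---|---|
| UCSB, MCI | 3 | 12 + 3 = 15 | 9×3 + 3×2.5 = 34.5 |
| UCSB, dementia | 3 | 12 + 3 = 15 | 9×3 + 3×2.5 = 34.5 |
| Rendever, MCI | 5 | 12 + 5 = 17 | 7×3 + 5×2.5 = 33.5 |
| Rendever, dementia | 5 | 12 + 5 = 17 | 7×3 + 5×2.5 = 33.5 |
| Total | 16 | 64/192 = 33.3% | 136/192 = 70.8% |

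**4. Is this particular to the trial?** No. Of the 6 block orders, 4 open mixed and 2 open with a pair. The expected share certain is (4×1 + 2×2)/(6×4) = 8/24 = 33.3%. The expected share guessed is (4×3 + 2×2.5)/(6×4) = 17/24 = 70.8%. The printed list equals both. The figures are also a ceiling, since they require someone to track every earlier assignment across about six communities per site.

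**5. Was enrolment still open when this text was written?** Section 1.2 gives losses before the end of the intervention as 20×2 + 2 = 42 of 372 people, and over the whole trial as 20×2 + 12 = 52 of 372. If all consented in pairs, 372/2 = 186 dyads, against 192 planned. Attrition over the whole trial, reported in the past tense, could not have been written before enrolment ended.

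**6. How open is the stratum label?** By the order of steps in section 10.1.1.2, MMSE-2 and AD8 are both done before the dyad is enrolled. Under section 8.2, senior personnel give the MMSE-2 and the adult child, not staff, completes the AD8. The remark about unreliable MMSE-2 scores is the reason given for adding the AD8. Some discretion remains near the boundary, but the number of such residents is not given. The differing MMSE-2 ranges (13 to 26 in section 2.3.3, 13 to 27 in section 5.1) concern the mild end of eligibility. They need reconciling separately and do not bear on the MCI/dementia cut.

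**7. Would an added balance check settle it?** Take MMSE-2 compared by arm within a stratum, 24 per arm, and a true imbalance of 0.5 SD. The standardized difference is 0.5 × √(24/2) = 1.73 against a critical value of 1.96, so power is about 40% at two-sided 0.05. Such a table would often miss a real imbalance, and it cannot detect selection on enrolment timing or on unmeasured traits.

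**The case for a change.** The strongest reply is that the section headed as the plan's measures against bias holds a list and nothing on concealment. The same site teams recruit, test, enrol and run the sessions, and one of them belongs to the developer of the product under test. The other safeguards (random choice among eligible adult children, approval by the community's Director and staff, testing before enrolment) do not govern when a dyad is enrolled or in what order residents are approached. Baseline surveys are also read aloud by staff to residents with dementia. Describing what was done would cost a paragraph.

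Much of this is fair. The gap is real, and a reader cannot judge concealment from these documents. Two parts carry less weight. The documents show the same teams, not the same individuals, in each role. The baseline point is also narrower than it looks: residents with MCI, half the planned sample, may complete surveys themselves with assistance (section 5.5), and adult children answer online (section 6.1.2).

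The decisive step, that enrolling staff could see the list, has no support in the text. Without it, what remains is a request for description, and the trial report can meet that. Section 9.4.1 already commits the trial to CONSORT reporting.

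**Conclusion.** This is missing descriptive detail and does not call for a change to the plan. The schedule is correctly built and balanced. The 33% and 71% figures are ordinary for fixed blocks of 4, and the 192/192 figure depends wholly on access that the documents do not show. If the list was properly held, the results stand as planned: analysts use the assigned arm, as section 9.4.1 requires, and the stratum recorded at randomization. Withdrawing the list or altering its release would very probably come too late, and an added balance table would reassure little.

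This rests on two assumptions: that enrolment is complete, which section 1.2 strongly suggests, and that nobody enrolling dyads used the list, which the documents neither confirm nor contradict. If the study team knows otherwise on the second, that is a limitation on the primary comparison for the report to state, along with who held the list and how MCI and dementia were told apart. The size of any resulting bias cannot be computed from these documents.

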6.4 Study Intervention/Experimental Manipulation Adherence

Participant adherence to the intervention will be tracked through weekly monitoring of technology session attendance. While sessions are expected to follow the intended schedule, flexibility is allowed for health-related absences or travel, with sessions rescheduled as needed to maintain engagement.

Survey completion is a required component of adherence monitoring. Residents will complete surveys with researchers to ensure data accuracy. Adult children will be verbally reminded at the end of each session to complete their surveys. Researchers will monitor survey completeness and provide up to three reminders via text, call, and/or email to encourage adult child participants to complete their surveys.

Study adherence records, including session attendance and survey completion tracking, will be maintained to assess participant engagement and intervention adherence throughout the study.

